6.4 EXPLORATORY ANALYSES 16

6.5 TOLERABILITY ANALYSES 16

7. SAFETY ANALYSIS.....	17
7.1 EXTENT OF EXPOSURE	17
7.2 ADVERSE EVENTS	17
7.2.1 Treatment-emergent Adverse Events	17
7.2.2 Adverse Event Severity	17
7.2.3 Adverse Event Relationship to Study Medication	18
7.2.4 Serious Adverse Events	18
7.2.5 Adverse Event Summaries	18
7.3 CLINICAL LABORATORY ASSESSMENTS	19
7.4 VITAL SIGNS.....	20
8. INTERIM ANALYSES	21
9. SAMPLE SIZE AND POWER CALCULATIONS	21
10. REFERENCES.....	21
11. APPENDIX.....	22
11.1 APPENDIX A: SCHEDULE OF EVENTS	22

LIST OF ABBREVIATIONS

Abbreviation	Definition
ACR	American College of Rheumatology
AE	Adverse Event
ANCOVA	Analysis of Covariance
ANSI	American National Standards Institute
AQL	Acceptable Quality Level
ATC	Anatomical, Therapeutic, and Chemical
AUC	Area under the concentration/time curve
BMI	Body mass index
BP	Blood pressure
BSP	Burning-stinging pain
CDA	Clinical Data Associate
CRO	Contract Research Organization
DLT	Dose-limiting toxicity
ECG	Electrocardiogram
eCRF	Electronic case report form
ESR	Erythrocyte-sedimentation rate
FSH	Follicle-stimulating hormone
ITT	Intent-to-treat
MedDRA	Medical Dictionary for Regulatory Activities
mITT	Modified Intent-to-Treat
NRS	Numeric Rating Scale
OA	Osteoarthritis
OAKP	Osteoarthritis knee pain
PP	Per Protocol
PT	Preferred term
QC	Quality control
RCTC	Rheumatology Common Toxicity Criteria
RDC	Remote data capture
RF	Rheumatoid factor
SAE	Serious adverse event

Abbreviation	Definition
SAF	Safety
SAP	Statistical Analysis Plan
SOC	System organ class
TEAE	Treatment-emergent adverse event
TESAE	Treatment-emergent serious adverse event
VAS	Visual Analogue Scale
WHO	World Health Organization
WOMAC	Western Ontario and McMaster Universities Index of Osteoarthritis

SAP REVISIONS

The following table details the changes made to the SAP version 1.0 (04OCT2018) to provide clarifications on the efficacy analysis.

Protocol Version #	SAP Section	Modification	Description and Rationale
5.0	List of Abbreviations	Added "PP" to the list	Updated for the analysis
5.0	4.2	Added the definition of Per Protocol analysis set and the corresponded analysis.	Updated to be consistent with the planned analysis for the study.
5.0	6.3	Updated the definition of durable clinical response.	Updated to provide clarifications.

1. INTRODUCTION

This statistical analysis plan (SAP) is based on the Protocol # VZU00025, titled “A Phase 2 Double-Blind Clinical Trial to Examine the Comparative Effects on Osteoarthritic Knee Pain of CGS-200-1 (1% Capsaicin Topical Liquid), CGS-200-5 (5% Capsaicin Topical Liquid), and CGS-200-0 (Vehicle, No Capsaicin).” See the study protocol for full details.

This document details the statistical methods planned to perform the final analyses of the study. This study will involve application of CGS-200-1 and CGS-200-5 (which has 1% and 5% capsaicin respectively) or of a Vehicle CGS-200-0 (which has no capsaicin in it). Study analysis will include comparison of the treatment effect on osteoarthritis (OA) knee pain as assessed by the Western Ontario and McMaster Universities Index of Osteoarthritis (WOMAC) score for OA signs and symptoms.

2. OBJECTIVES AND ENDPOINTS

2.1 Objectives

The objectives of the present study are the following:

- To develop pain relief dose-response data for osteoarthritis knee pain (OAKP), compared to Vehicle, for the following concentrations of Capsaicin in CGS-200 vehicle: 1% and 5% using the WOMAC pain subscale (VAS formatted) as the primary pain index for relief of OAKP.
- To confirm, in a U.S. based population, the high safety profile for CGS-200-5 that was reported in Studies VZU00021 and VZU00023 in a Dominican Republic population.
- To develop data for relief of signs and symptoms of osteoarthritis using the WOMAC subscales for pain, stiffness and function and total WOMAC score.
- To develop OAKP relief data using the 100 mm VAS scale.

2.2 Endpoints

2.2.1 Primary Efficacy Endpoint

The primary efficacy endpoint of this study will be to examine the extent of reduction in the WOMAC pain score, relative to baseline, provided by once daily, one-hour application of Vehicle (CGS-200-0), CGS-200-1 and CGS-200-5 at the following assessment times:

Baseline: \leq 30 minutes prior to first daily application

Day 35: 31 Days (+/- 3 days) after fourth daily application

and based thereon to determine whether the responses for treatment with CGS-200-1, and CGS-200-5 are significantly different from Vehicle (CGS-200-0) and from each other at the primary endpoint time.

2.2.2 Secondary Efficacy Endpoints

The secondary efficacy endpoints will be:

- (1) To examine the extent of reduction in the WOMAC pain score, relative to baseline, provided by once daily, one-hour application of Vehicle (CGS-200-0), CGS-200-1, and CGS-200-5 at the following assessment times:

Baseline: \leq 30 minutes prior to first daily application

Day 5 24 hrs (+/- 3) after the last of the 4 daily applications

Day 19 15 days (+/- 3) after the last of the 4 daily applications

Day 64 60 days (+/- 3) after the last of 4 daily applications

Day 94 90 days (+/- 3) after the last of 4 daily applications

- (2) Day 5, 19, 35, 64, and 94 WOMAC scores on the stiffness and function subscales as well as total WOMAC score (including the WOMAC pain score).

2.2.3 Primary Safety Endpoints

The primary safety endpoints will be:

- (1) The application of the study drug does not produce skin reactions (erythema, scaling, pruritus, or other) to a degree that is clinically of concern. Scoring of erythema and scaling at the application sites and of pruritus will be assessed per the scoring systems in the Protocol Appendix G.
- (2) No SAE's either possibly, probably or definitely associated with study treatments.
- (3) Safety labs (hematology, serum chemistry and urinalysis) do not produce other than minimal – mild toxicities (Grade 1 or Grade 2). Scoring of clinical, hematological and urinalysis out of range findings for toxicity grading will be per the Protocol Appendix B.

2.2.4 Secondary Safety Endpoints

The secondary safety endpoints will be:

- (1) The distribution by study arms of specific Adverse Events (AEs) (i.e.: local application site reactions), and other AEs (inclusive of findings for hematology, serum chemistry and urinalysis).
- (2) Evaluate the amount of concomitant pain medications used overtime.

2.2.5 Tolerability Endpoints

The tolerability endpoints (which are secondary in nature) will be:

- (1) The application of study drug does not produce burning-stinging pain (“BSP”) at the application site to a degree that is not acceptable to the subject. BSP at the application site, this will be assessed using a 0 – 10 Numeric Rating Scale (NRS) scale without guideposts. “Acceptability” of BSP will be queried per subject at the end of each application period.
- (2) The application of the study drug does not produce pruritus during application or in the 24 hrs post-application to a degree that is not acceptable to the subject or, if bothersome to the subject, cannot be managed by application of ice or a cold pack or compress.

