APPENDIX C SCHEDULE OF EVENTS

APPENDIX C: SCHEDULE OF EVENTS

Assessment	SCR	Treatment Days			Follow-up Period Days						
TIMEFRAME	Within 28 days of Day 1	D1	D2	D3	D4	D5 (Post Treat Day 1)	D19± 3d (Post Treat Week 2)	D35±3d (Post Treat Week 4)	D64± 3d (Post Treat Week 8)	D94± 3d (Post Treat Week 12)	Unscheduled, Early Termination, SAE ¹
Clinic visit	X	X	X	х	X	X	X	X	X	X	X
Informed Consent	X										
Inclusion / Exclusion	X										
Demographics	X										
Medical & Medication History	X										
Randomization		X									
Physical exam	x										X
Height and Weight ^a	X										
Vital Signs ^b	X	X	X	X	X	X				X	X
Knee X-rays ^c	X										
12-lead ECG ^d	X										
Clinical lab tests ^e	X					X		X		X	X
Pregnancy or FSH Test ^f	X	X									
Application Site Pain, Erythema, Scaling, Pruritus Assessment ^g	X	x	x	x	x	X	X	X	X	X	X
Exploratory Assessment of OA Knee Painh	X	X									
VAS OA Knee Pain Assessment ⁱ		X	X	X	X	x	X	X	X	X	X
WOMAC ^j	X	X				X	X	X	X	X	X
Drug administration		X	X	х	X						
Assess. Of Concomitant Medications ^k	X	X	X	X	X	X	X	X	X	X	X
AE Assessments		X	X	X	X	X	X	X	X	X	X
Study Exit										X	

Schedule of Events (Continued)

- a. Height and weight obtained at Screening.
- b. Vital signs include temperature, blood pressure, heart rate and respiratory rate. Performed at Screening, on Days 1-4 at pre-dose and at 90 minutes (± 5 min) after applying study drug to knees, and at Follow-up on Day 5 and 94.
- c. Knee X-rays of both knees must be obtained unless films/images performed within 6 months before screening. Copies of film and results will be requested.
- d. Standalone 12-lead ECG performed at Screening.
- e. Clinical laboratory tests include (Appendix A):

Hematology: full blood count including RBC, hemoglobin, hematocrit, MCV, MCH, MCHC, WBC, differential white cell count, platelet count (Screening, Day 5, Day 35 and Day 94);

Erythrocyte sedimentation rate (Screening only);

Chemistry: BUN, creatinine, uric acid, bilirubin (total), sodium, potassium, calcium, magnesium, phosphorous (inorganic), chloride, bicarbonate, ALK, AST (SGOT), ALT (SGPT), LDH, GGT, CPK, albumin, total protein, and glucose (Screening, Day 5, Day 35 and Day 94);

IgM RF (Screening only);

Urinalysis: pH, protein, glucose, ketones, bilirubin, blood, urobilinogen, specific gravity, leucocytes (Screening, Day 5, Day 35 and Day 94). Clinically significant abnormal dipstick results will require microscopic analysis.

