APPENDIX F ASSESSMENT OF BURNING / STINGING PAIN

APPENDIX F: ASSESSMENT OF BURNING / STINGING PAIN

Obtained on Days 1-4: Pre-application (< 30 min), and at 15 (+ 5 min), 30 (+ 5 min), 60 (+ 5 min), and 90 minutes (+ 5 min) after application, and on Days 5, 19, 35, 64 and 94.

Assessment of Burning / Stinging Pain

The question below refers to BURNING OR STINGING PAIN that you may be feeling right now affecting the skin in the area around your knees.

On a scale from 0 to 10, with 0 being no pain at all and 10 being the worst pain imaginable, how would you rate your pain RIGHT NOW in your RIGHT KNEE? (Please circle the number)

0 1 2 3 4 5 6 7 8 9 10 No Worst Pain Pain Imaginable

On a scale from 0 to 10, with 0 being no pain at all and 10 being the worst pain imaginable, how would you rate your pain RIGHT NOW in your LEFT KNEE? (Please circle the number)

0 1 2 3 4 5 6 7 8 9 10 No Worst Pain Pain Imaginable

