APPENDIX G ASSESSMENT OF SIGNS AND SYMPTOMS

APPENDIX G: ASSESSMENT OF SIGNS AND SYMPTOMS

Obtained on Days 1-4: Pre-application (\leq 30 min), and at 15 (\pm 5 min), 30 (\pm 5 min), 60 (\pm 5 min), and 90 minutes (\pm 5 min) after application, and on Days 5, 19, 35, 64 and 94.

Assessment of Signs and Symptoms

Right Knee	Left Knee				
Scaling (Circle Response):	Scaling (Circle Response):				
0 = None: no evidence of scaling	0 = None: no evidence of scaling				
1 = Mild: mainly fine scales predominate	1 = Mild: mainly fine scales predominate				
2 = Moderate: somewhat coarser scales	2 = Moderate: somewhat coarser scales				
3 = Severe: coarse, thick scales; rough surface	3 = Severe: coarse, thick scales; rough surface				
Erythema (Circle Response):	Erythema (Circle Response):				
0 = None: no evidence of redness	0 = None: no evidence of redness				
1 = Mild: barely perceptible redness	1 = Mild: barely perceptible redness				
2 = Moderate: obvious redness, possible presence of edema	2 = Moderate: obvious redness, possible presence of edema				
3 = Severe: bright red, possible edema	3 = Severe: bright red, possible edema				
Pruritus (Circle Response):	Pruritus (Circle Response):				
0 = None: no itching	0 = None: no itching				
1 = Mild: occasional, slight itching	1 = Mild: occasional, slight itching				
2 = Moderate: frequent or constant itching; does not disturb sleep	2 = Moderate: frequent or constant itching; does not disturb sleep				
3 = Severe: bothersome itching; disturbs	3 = Severe: bothersome itching; disturbs sleep				

sleep

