6.5 Tolerability Analyses

The primary tolerability endpoint will be tolerability of the formulations on each of Days 1, 2, 3, and 4. On each of these days, subjects will report an NRS score for burning / stinging at the application site pre-treatment and during treatment, and a pre-treatment and during treatment pruritus score. Pre-treatment and during treatment erythema and scaling scores will be recorded by clinic staff assigned to the study. This will be done at 0, 15, 30, 60, and 90 minutes after application to capture time points during treatment and after washing the application site. The score for each of the above tolerability variables will be entered as a value at each assessment time.

For each subject, an area under the curve (AUC) calculation will be performed in 90 minute intervals for each score value. The AUC for a specified time interval will be calculated using the

trapezoidal rule. If we have $n+1$ measurements y_i at times t_i ($i=0, 1, \dots, n$), then the AUC is calculated as $AUC = \frac{1}{2} \sum_{i=0}^{n-1} (t_{i+1} - t_i)(y_i + y_{i+1})$.

For each of Days 1 through 4, the average of AUC from left and right knees will be calculated for each of the tolerability variables. The calculated average of AUC from all the tolerability variables will then be combined and compared between each Active Treatment Arm (CGS-200-5 and CGS-200-1) and the Vehicle Arm (CGS-200-0) using analysis of variance (ANOVA).

A listing will be provided for all the tolerability variables at each visit.

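### Both tolerability endpoints are defined by what the subject finds acceptable, but the stated analysis is a 90-minute severity AUC, and for pruritus no acceptability question is specified anywhere

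*SAP*

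**What the plan says.** Protocol 2.2 and SAP 2.2.5 set two tolerability endpoints, described as secondary. The first is that BSP does not reach a level the subject finds unacceptable. It is to be rated on a 0–10 NRS, and acceptability "of BSP will be queried per subject at the end of each application period". The second is that pruritus, while the drug is on and over the following 24 hours, is not unacceptable to the subject or, if bothersome, is not such that it "cannot be managed by application of ice or a cold pack or compress". No query is attached to the second endpoint.

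The reproduced forms record severity. Protocol Appendix F asks "how would you rate your pain RIGHT NOW in your RIGHT KNEE" on a 0–10 scale, and the same for the left knee. Protocol Appendix G grades scaling, erythema and pruritus from 0 to 3, with pruritus categories such as "2 = Moderate: frequent or constant itching; does not disturb sleep". The row in the Schedule of Events is "Application Site Pain, Erythema, Scaling, Pruritus Assessment".

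For analysis, SAP 6.5 names BSP, pruritus, erythema and scaling scores at 0, 15, 30, 60 and 90 minutes and states "The score for each of the above tolerability variables will be entered as a value at each assessment time". It then says "The calculated average of AUC from all the tolerability variables will then be combined and compared between each Active Treatment Arm" and the vehicle arm, by ANOVA. The only other output there is "A listing will be provided for all the tolerability variables at each visit". Protocol 9.5.4 also relies on a combined AUC.

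**The concern.** The endpoint and its named analysis are different quantities. A subject may rate burning as 7 and accept it for the sake of relief, or rate it as 4 and refuse another application. Neither document gives a rule that turns a score into an acceptable or unacceptable response.

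Acceptability is also the more informative question. Protocol 1.3 reports BSP in 100% of CGS-200-5 subjects and 35% of vehicle subjects in Study VZU00023, so a difference in severity between arms is largely expected. Whether subjects would tolerate the burning is less certain, and SAP 6.5 does not address it.

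A judgement made at the end of an application cannot be reliably reconstructed months later, so an unasked question would leave a permanent gap.

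**Working it through.** The plan states no figure for acceptability, so there is none to reproduce. The check traces each endpoint from definition to analysis, then asks whether the AUC could stand in for it.

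**Trace**

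| Step | BSP | Pruritus |
|---|---|---|
| Endpoint (Protocol 2.2, SAP 2.2.5) | Acceptable to the subject | Acceptable to the subject through 24 h; if bothersome, manageable with cold |
| Query required in the text | Yes, per subject, after each application | None |
| Reproduced form | Appendix F: severity 0–10 per knee | Appendix G: severity 0–3 per knee |
| Protocol Tables 6-2 and 6-3, both schedules | Severity only | Severity only; use and effect of cold not listed |
| Named analysis (Protocol 9.5.4, SAP 6.5) | Severity AUC, 0–90 min | Severity AUC, 0–90 min |
| Rule from score to unacceptable | None | None |

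**Can the AUC stand in for acceptability?** SAP 6.5 uses the trapezoidal rule, AUC = ½ Σ (t[i+1] − t[i])(y[i] + y[i+1]), on times 0, 15, 30, 60 and 90.

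1. *Content.* The SAP does not say how the AUCs are combined; assume a simple sum. The maximum is 10 × 90 = 900 for BSP and 3 × 90 = 270 for each of the other three, so 900 + 3 × 270 = 1710. BSP is 900/1710 = 52.6%, pruritus 270/1710 = 15.8%, and erythema plus scaling 540/1710 = 31.6%. These are shares of the attainable maximum, not of expected data.
2. *Ranking.* A BSP profile of 0, 10, 0, 0, 0 gives ½[15×10 + 15×10] = 150. A profile of 0, 2, 2, 2, 2 gives ½[15×2 + 15×4 + 30×4 + 30×4] = 165. The AUC therefore ranks a brief spell of the worst imaginable pain as better tolerated than mild discomfort throughout.
3. *Window.* The AUC ends at 90 minutes. If the 24 hours (1,440 minutes) run from application, it covers 90/1440 = 6.25% of them. If they run from wash-off at 60 minutes, it covers 30/1440 = 2.1%. A severity score is taken before the next application and at the Day 5 visit, but each is a rating at one moment.

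**Precision if acceptability were tabulated.** This is a Clopper–Pearson 95% interval: lower limit = Beta quantile(0.025; x, n−x+1), upper limit = Beta quantile(0.975; x+1, n−x). Take n = 40 per arm, the evaluable target in SAP Section 9. The counts are assumptions, because the documents give no expected rate.

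| Not acceptable | Percent | Exact 95% interval |
|---|---|---|
| 0/40 | 0% | 0 to 8.8% |
| 4/40 | 10% | 2.8 to 23.7% |
| 8/40 | 20% | 9.1 to 35.6% |

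**The case against.** The strongest reply concerns BSP. The endpoint text is itself an instruction to collect: it names the respondent, the timing and the frequency. A site that follows it asks the question. The appendices are not the full set of forms either; the WOMAC, the primary instrument, is not among them. Protocol 10.5 refers to a sponsor-supplied Data Sheet for tolerability variables, and neither it nor the eCRF is shown. The protocol synopsis promises descriptive tables for the tolerability endpoint, and SAP Section 4 summarises categorical variables by number and percentage per treatment group, so a recorded yes/no answer would have a default table. Intensity also belongs to the BSP endpoint, since the NRS is its named rating. SAP 7.1 summarises why a full dose was not applied, and SAP 7.2.5 lists treatment given for adverse events.

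Most of this stands for BSP. A reader might infer that the trial will end with no acceptability data, or that neither endpoint has any planned analysis. The documents do not support either inference: the BSP query is required, the collection tools cannot be inspected, and the general descriptive statements exist.

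The reply does not reach the rest. The general statements do not name acceptability, and SAP 6.5, which should, specifies something else. For pruritus there is no instruction to ask, so a default table would have nothing to summarise. Reasons for incomplete dosing are indirect, because a subject can complete dosing and still find it unacceptable.

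**Conclusion.** The concern holds, with different force for the two endpoints. For both, the named analysis is a 0–90 minute severity AUC that does not measure acceptability and mixes in erythema and scaling, which are in neither endpoint. For BSP, the query is required in the text but is not carried onto any reproduced form or schedule row and is not named in SAP 6.5; the gap is one of traceability and of a missing specific analysis. For pruritus, the endpoint cannot be answered from the plan as documented, because no question on acceptability or on management with cold is specified.

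The 31.6% share rests on a simple-sum reading of the combination. The intervals describe what the remedy would deliver at assumed counts; they are not the size of an error. SAP Section 6 places tolerability on the safety set, which may exceed 40 per arm given the replacement allowance. As the endpoints are secondary and SAP 4.5 calls the study exploratory, this should be corrected but does not threaten the primary result.

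**What to change.** Collection: add to the form and both schedules, or cite the Data Sheet if it already holds them:

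- one yes/no item per subject at the end of each application on Days 1–4, on whether the BSP was acceptable;
- pruritus items across Days 1–5: acceptable during the application (Days 1–4), acceptable over the past 24 hours (before application on Days 2–4 and at the Day 5 visit) and, if bothersome, whether cold managed it, yes/no.

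Analysis: in SAP 6.5, tabulate the number and percent not acceptable by day and ever, by arm, on the safety set, with exact 95% confidence intervals. Do the same for pruritus not managed by cold. Label the AUC comparison as supportive and state how the component AUCs are combined.

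Cost: a small added question burden at visits that already take place on Days 1–5, and one extra table. No additional visit is needed.

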3. INVESTIGATIONAL PLAN

3.1 Study Design

This is a multi-center, randomized, double-blind clinical trial to examine the comparative effects on OAKP of CGS-200-1 (1% Capsaicin content) (N=40), CGS-200-5 (5% Capsaicin content) (N=40), and CGS-200 Vehicle (no Capsaicin) (N=40) in subjects with OA of the knees according to the 1986 American College of Rheumatology (ACR) criteria. Assigned doses will be applied at the clinic for 60 minutes on each of four consecutive days.

Subjects who meet the inclusion/exclusion criteria specified in the Protocol, Section 4.1 will be randomized to one of the three Arms in this study: CGS-200-1 or CGS-200-5 or CGS-200-0 (Vehicle) in a 1:1:1 ratio. All subjects will receive 4 consecutive days of treatment and will then be followed up until the Day 94 visit.

Even though both knee(s) will receive application of study test materials, with regard to reduction in WOMAC pain and VAS pain score associated with study treatments, only one knee will be indicated as the “Study Knee”. This will be the knee with the highest WOMAC pain score at baseline. If both knees have equal WOMAC pain scores at baseline, then the right knee will be considered the “Study Knee” with regard to WOMAC pain and Visual Analogue Scale (VAS) pain score reduction.

Data will be collected from Day 1 through Day 5 and then again on Days 19, 35, 64 and 94 for efficacy, tolerability, and safety measures. See Appendix C for the Schedule of Events.

3.2 Treatment

3.2.1 Randomization Scheme and Treatment Arm Assignment

Subjects will be randomly assigned to receive CGS-200-1, CGS-200-5 or CGS-200-0 in a 1:1:1 ratio. Subjects that do not receive 4 complete consecutive daily doses and/or drop out before completing the Day 35 visit may be replaced if the reason for dropping out is other than lack of drug product tolerability. A dose will be considered complete when at least 80% has been delivered on any study drug administration day; dosing will be considered complete overall when a total of at least 80%, in the aggregate, has been delivered across all study treatment days. Subjects that drop out or who cannot be followed up from after the Day 5 visit until the Day 35 visit may be replaced. Up to 10 subjects per arm may be replaced.

